### 8.2 Transposable elements assay

In order to fulfil the secondary outcome of the study, we will randomly select a total of 100 samples (25 samples from patients with confirmed CRC and 75 non-cancer

Plasma biomarkers in stratifying patients referred via the lower gastro-intestinal (LGI) suspected cancer two-week wait (2WW) pathway

V5 7th of April 2025

(normal) samples) out of the original cohort of 582 participants. The plasma from this sub-population of 100 patients will be subjected to RNAseq analysis looking for transcript signatures to identify potential transposable elements. Also Plasma DNA will be used for nanopore DNAseq (provides sequence variants and epigenetic modifications of DNA). The TEs identified in this project to predict CRC will be also validated by testing it on publicly available additional cfRNA cohorts (http://111.198.139.65/cfomics/source) for CRC prediction.

The study will be a single centre, pilot, cohort observational study performed within the setting of the NHS. Indemnity will be provided by Queen Mary University of London. However, there is no harm that can be foreseen from enrolment into this study as the only intervention is a blood draw done during routine intravenous cannulation for the standard clinical care. There is no IP opportunity from the PG assay study. The PG blood test is a commercially available assay. However, the use of TE as a biomarker for colorectal is a relatively new field and the investigators will explore the possibilities for IP. No samples from this study will be stored by Progastrin Manufacturing, Biodena Care, [name]. Any remaining plasma samples after the PG assay will be returned to the study team and will be stored at QMUL National Bowel Research Centre (NBRC), Blizard Institute and used by the research team at QMUL, for future research studies. Any future studies will have Ethics Committee permission. Patient clinical data will be securely destroyed at the end of the research studies. All staff undertaking future studies will abide by the Data Protection Act 1998 with any medical information relating to you being kept confidential.

# 9. Study procedures.

[figure not shown]

Step IV

A pilot feasibility study to determine the predictive value of plasma biomarkers in stratifying patients referred via the lower GI suspected cancer (two-week wait) pathway

2WW referrals list

ticipant information sheet

Introduce the trial during Hospital

Step II

Gain consent and proceed for collection of 20 mL of peripheral venous blood sample from the patient during the venous access at their referred investigation (Colonoscopy or Cross-sectional imaging)

Step III

Collection, Storage within Blizard Institute Lab and Dispatch batches of 100 blood samples to the testing facility based in France.

Lab and E-Questionnaire followed by Data completion, analysis at publication of the results

Step V

Telephone follow-up after 72 hrs to respond to questions Remaining plasma samples will be used for analysis of RNAseq for transcript signatures as well as plasma DNA for nanopore DNAseq.

Study procedures are displayed below in the flow-chart.

Enrolment to the study is anticipated to take four to five months or until 582 participants are recruited with subsequent analysis available when a histological diagnosis of cancer is confirmed or refuted after appropriate investigation on the pathway. Analysis will then take a further two to three months. Patients will be numbered according to a random number generation to maintain confidentiality and anonymity. Samples will be labelled only with the appropriate trial number. Informed consent will be recorded in written form and a copy uploaded to the patients electronic health records (EHR).

Personal data pertaining to this study will be accessed for six months after the study closes and data kept for independent review for 5 years. This will be under the personal supervision of the principal investigator and kept in a secure lockable office and on Trust password-protected computers. Participants and investigators will not receive payment for this study. The study is funded by a research grant from LAPResearch UK (registered charity number: 1130523), a charitable trust.

Patients will be screened for suitability and recruited to the study within the 2WW clinic. Upon the receipt of informed consent, patients' medical history and a blood sample will be taken. This includes initials, date of birth, sex, BMI, ethnicity, height, and weight, to be recorded on the CRF. The blood sample will be transported to and processed to extract the plasma and stored in the laboratories at the Blizard Institute based at the NBRC, [name]. Batches of 100 fully anonymised plasma samples will be sent to Progastrin Manufacturing, Biodena Care, [name] for the plasma progastrin assay. The remaining unused plasma will be stored in Blizard Institute, Whitechapel, London lab and will be used for RNAseq analysis for transcript signatures to identify potential transposable elements and nanopore DNAseq to provide sequence variants and epigenetic modifications of DNA. The latter assay's will be conducted at the Blizard Institute laboratories.

The plasma progastrin levels will be sent back to the study team at Queen Mary University of London based at the NBRC, [name] by the Progastrin Manufacturing team, Biodena Care [name], [name] and will be added to the study database. Participants are free to withdraw from the study at any time and will be provided with reassurance that this will not affect their care in any way.

Before enrolment into the study, participants will be fully informed of the nature of the study and all relevant aspects of study procedures. It is the investigators' responsibility to explain the nature of the study, its purpose and associated procedures, the expected duration and the potential benefits and risks of participation to each subject prior to their entry into the study (i.e. before examinations and procedures associated with selection for the study are performed).

Each prospective participant will be provided with the Patient Information Sheet and Informed Consent Forms that are to be compiled as one integrated document. Each subject will be given a minimum of 24 – 48 hours to study the provided information and to ask questions and will be informed about their right to withdraw from the study at any time without any disadvantage and without having to provide reasons for their decision. Once the essential study information has been provided and the Investigator

Plasma biomarkers in stratifying patients referred via the lower gastro-intestinal (LGI) suspected cancer two-week wait (2WW) pathway

V5 7th of April 2025

is assured that each individual patient understands the implications of participating in the study, the eligible patients who pass the screening evaluation will be recruited. Consent Forms shall be signed and dated by the appropriate parties. A notation that written informed consent has been obtained will be made on the and a record made in their clinical notes. Completed Consent Forms will be retained by the Investigator, a copy entered into the clinical notes, and a copy will be provided by the Investigator to the patient. The Informed Consent Form is included as part of the submission to the Ethics Committee.

The informed consent form and any other written information provided to subjects will be revised whenever important new information becomes available that may be relevant to the subject's consent, or there is an amendment to the protocol which necessitates a change to the content of the subject information and/or the written informed consent form. The investigators will inform the subject of changes in a timely manner and will ask the subject to confirm to continue their participation in the study by their signature on the revised informed consent form. Any revisions to the written informed consent form, and written information will receive main REC approval in advance of use. Patients will be free to withdraw at any time without affecting their healthcare or legal rights.

Participants will be informed that their data are held on file, that these data may be viewed by the Sponsor and by external auditors on behalf of either the sponsor or regulatory agencies. They will similarly be informed that this data and a report of the study will be submitted to the Sponsor and may also be submitted to government agencies and perhaps for publication, but that they will only be identified in such reports by their study identification number. The investigators undertake to hold all personal information in confidence and in compliance with the Data Protection Act 2018 and Caldicott committee.

A study specific database will be created on the REDCap (QMUL approved) and will be used for all study purposes. The access to the study REDCap database will be strictly limited to the core study team (CI, PI and RF) and will be password protected.

Trial termination is guided by: 1) complete data collection (primary & secondary outcomes) for minimum of 582 participants, ensuring sufficient data to address research questions; 2) mandated follow-up periods for specific trials; 3) post-recruitment data analysis for robust findings; 4) regulatory/ethical committee requirements; and 5) resource constraints for efficient allocation.

The end of the study will represent recruitment complete analysis of both plasma progastrin and TE of 582 plasma samples.

#### 10. Statistical considerations

Our study aims to evaluate the potential utility of PG levels as a novel biomarker to predict CRC diagnosis in patients referred via the 2WW and STT suspected cancer

Plasma biomarkers in stratifying patients referred via the lower gastro-intestinal (LGI) suspected cancer two-week wait (2WW) pathway

referral pathways. The study population will be drawn from the Barts Health NHS Trust catchment area. Barts Health NHS Trust have five different sites of which three sites (Royal London Hospital, Whipps Cross Hospital and Newham University Hospital) receive 2WW/STT referrals. Approximately, some 7,030 patients are referred via the 2WW/STT from primary care to the secondary care with the suspicion of lower gastrointestinal (GI) cancers every year.

The current feasibility study aims to recruit the study participants from the Royal London Hospital site of Barts Health NHS Trust, and can be expanded to other sites within the trust if recruitment becomes challenging within the stipulated recruitment timeframe of the study. The department at the Royal London Hospital receives around 50 new two week wait referrals every week (200 new patients per month), giving approximately 2,400 (34% of the total BHT referrals) potential patients to be screened for the study. Roughly, 9.5% of 2WW referral patients will have a colorectal cancer confirmed as per our local data. Anticipating a minimum recruitment period of 18 weeks, we will recruit 582 eligible patients from the screened 2WW/STT population at the Royal London Hospital. This sample size, was adjusted for a 30% screening failure rate and is expected to yield approximately 55 CRC cases and 527 control subjects from the study population to test the hypothesis of PG as a potential biomarker for CRC diagnosis in 2WW/STT patients.

The secondary outcome of identification and proof of principle validation of circulating TE as a potential novel biomarker for CRC is exploratory and hence does not require formal power calculation. Instead, for this exploratory study we will select a sub-set of 100 (25 proven CRC and 75 non-cancer (normal) patient samples from the 582 study cohort for RNAseq and DNAseq analyses.

#### 10.1. Sample size

Approximate Annual Referral Volume for RLH ≈ 2400 patients per year Recruitment Period:18 weeks (4-5 months)

Eligible Patients:

18 weeks \* (2400 patients/year / 52 weeks ) ≈ 831 eligible patients

Screen Failure:

30% screen failure rate

Potentially 70% of eligible patients enter the study: 831 \* 0.7 ≈ 582 patients

Case and Control Allocation:

Based on cancer office for LGI approximately 9.5% of lower GI patients have a cancer hence:

Cases: 9.5% of 582 ≈ 55 patients with LGI cancer

Controls: (100-9.5)% of 582 ≈ 527 patients without LGI cancer - assuming no other

cancers are detected

Plasma biomarkers in stratifying patients referred via the lower gastro-intestinal (LGI) suspected cancer two-week wait (2WW) pathway

V5 7th of April 2025

Sensitivity and Specificity of PG:

The sensitivity of the PG test is estimated to be between 70% and 87% at a cutoff of 0.2 pM. The specificity of the test at this cutoff is 97.5%.

Statistical Power and Significance Level:

To ensure adequate statistical power, we aim to achieve a power of 0.8 and a significance level of 0.05.

Receiver Operating Characteristic (ROC) Curve Analysis:

A power calculation was performed using the pROC package in R. The following parameters were used:

Number of cases (GI cancer): 55 Number of controls (no cancer): 527 Area under the curve (AUC): 0.6118569

Power = 0.8

To address the secondary outcome of the study a random number of 100 samples out of 582 number of samples (25 LGI cancer proven samples and 75 non-cancer (normal) samples) will be selected and tested for TEs in order to identify and validate novel biomarkers as potential tests for colorectal cancer diagnosis

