This is because the Wnt / b cadherin pathway coding for b cadherin is abnormal in many GI cancers. A further target of this pathway is the gene encoding PG. PG is converted to gastrin in normal healthy people (and is therefore undetectable) but can be detected in the plasma of many patients with both early and advanced GI malignancy. A study of colorectal polyps and cancers demonstrated an elevated level of PG in cancer subjects compared with benign polyps. Moreover, cancers going on to develop liver metastases produce higher PG levels in plasma. The sensitivity varies between different cancer types but in upper GI and CRCs is 80-95%. This is comparable to "missed" cancers at colonoscopy (3.5%).

Beyond progastrin, transposable elements (TEs), mobile genetic elements that can disrupt gene function, have emerged as promising candidates for cancer biomarker development. Recent research has identified TEs associated with various cancers, including CRC9. However, the role of TEs in predicting CRC diagnosis in 2WW referral cohorts remains underexplored. Liquid biopsy approaches, such as the analysis of circulating free nucleic acids (cfDNA and cfRNA) in conjunction with machine learning algorithms, have shown promise in cancer detection. These methods offer a less invasive alternative to traditional biopsies. Notably, recent studies, including those conducted by the [name] lab, have demonstrated that transposable element-derived RNA signatures can be superior predictors of diseases like pre-eclampsia and cancers. While these findings are encouraging, further research is required to establish the sensitivity and specificity of liquid biopsy approaches for CRC diagnosis. Independent cohort studies encompassing diverse ethnic populations are essential to ensure the generalisability of these methods. Moreover, multi-omics approaches, integrating data from various molecular levels, could enhance the diagnostic accuracy of liquid biopsy assays.

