Given that over 90% of patients referred to the lower GI cancer pathway will not have cancer, a screening test or tests to rule out cancers would reduce the burden on NHS targets and could be cost effective at excluding unnecessary tests. The most useful group to be tested and excluded from the pathway in the future would be those patients where the index of suspicion is low. These include those without a family history of CRC, ages between 18 and 55 (not yet eligible for CRC screening programme), no weight loss, good performance status of 0-1 and no history of inflammatory bowel disease.

Global CRC screening programs aim for a 65% participation rate, a target met in many European nations and reaching 74% in the USA. However, CRC screening lags behind breast and cervical cancer screening, which typically exceed 70% participation. A significant barrier to CRC screening is the low attendance rate for colonoscopy or CT colonography following abnormal faecal immunochemical tests (FIT) or faecal occult blood tests (FOBT), ranging from 10% to 30%. This low attendance is often attributed to negative experiences, word-of-mouth discussion, and sociocultural factors.

As emerging technologies like liquid biopsy, utilising biomarkers such as progastrin or transposable elements, offer potential for non-invasive CRC detection, understanding patient preferences for different screening modalities becomes crucial. These tests

vary in invasiveness, frequency, and risk profiles, and their effectiveness in altering risk profiles of CRC differs.

To optimise patient adherence and early detection, it is essential to identify the factors that influence patient choice among these diverse diagnostic options.

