# 6. Study objectives

#### 6.1. Primary objective

The primary objective of this study is to test whether plasma PG levels accurately predict the diagnosis of CRC and or polyps in a group of 2WW patients undergoing the standard investigations. The study will also aim to distinguish the absence of cancer by virtue of actual levels of plasma PG. To determine the sensitivity and specificity of plasma PG levels in patients with colorectal cancer (CRC), and benign colonic polyps when investigated via a 2WW referral pathway

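### Are 582 patients too few because the only power calculation tests the AUC against 0.5?

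*Protocol*

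**What the plan says.** Section 10.1 derives the sample size from accrual: 18 weeks of referrals at one hospital, less 30% screen failures, gives 582. At 9.5% prevalence this means about 55 cancers and 527 controls. It then states an aim, "To ensure adequate statistical power, we aim to achieve a power of 0.8 and a significance level of 0.05", and reports a calculation in pROC with "Number of cases (GI cancer): 55 Number of controls (no cancer): 527 Area under the curve (AUC): 0.6118569". The same section gives the expected accuracy, "The sensitivity of the PG test is estimated to be between 70% and 87% at a cutoff of 0.2 pM", with specificity 97.5%, but does not use it in the calculation.

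Section 9 lists conditions for ending the study. The first is "complete data collection (primary & secondary outcomes) for minimum of 582 participants, ensuring sufficient data to address research questions".

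The aims are wider than beating chance. Section 5.1 gives the intended use: "a screening test or tests to rule out cancers would reduce the burden on NHS targets". Section 6.1 adds: "The study will also aim to distinguish the absence of cancer by virtue of actual levels of plasma PG". Section 5.1 also says "The sensitivity varies between different cancer types but in upper GI and CRCs is 80-95" per cent, and follows this with "This is comparable to 'missed' cancers at colonoscopy (3.5" per cent).

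Sections 8.2, 9 and 10 call the study a pilot or feasibility study. The primary endpoint (6.4) and primary analysis (10.2) cover predictive values and the ROC curve; 10.2 adds sensitivity, specificity, accuracy and likelihood ratios.

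**The concern.** A reader may take the adequate-power statement in 10.1 and the sufficiency statement in section 9 to cover the whole primary objective. The one sized test asks only whether the AUC exceeds 0.5, and it becomes significant at an observed AUC of about 0.58. A test that weak would be of little use for ruling out cancer. Section 20 says positive findings will feed discussion of an extended study or a change to the pathway, and the protocol does not define a positive finding. A near-useless marker might therefore be reported as a success.

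In the other direction, if the 3.5% miss rate were the standard to meet, 55 cancers could not show that it had been met, even with none missed. The comparison in 5.1 also fits poorly with the protocol's own sensitivity figures.

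**Working it through.** **Inputs.** From section 10.1: 55 cases, 527 controls, AUC 0.6118569, power 0.8, alpha 0.05, sensitivity 70-87%, specificity 97.5%, prevalence 9.5%. From section 5.1: sensitivity 80-95%, colonoscopy miss rate 3.5%. The null value and the sidedness are not stated; they are inferred from the match in step 2.

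**1. The sample size.** 18 × 2400/52 = 830.8, taken as 831; 831 × 0.7 = 581.7, taken as 582; 582 × 0.095 = 55.3. All match.

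**2. The AUC figure.** Obuchowski one-ROC formula, null 0.5, two-sided 0.05, k = 527/55 = 9.58:
- Null variance term: 0.0792 × (1 + 1/9.58) = 0.0875.
- A = 1.414 × probit(0.6118569) = 0.402. Alternative variance term: 0.0099 × exp(−A²/2) × [(5A² + 8) + (A² + 8)/k] = 0.0882.
- z for power = (0.1118569 × √55 − 1.96 × √0.0875)/√0.0882 = 0.841, so power = 0.7999.

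Running the pROC power function with 55, 527, 0.8 and 0.05 returns 0.6118569 exactly. A one-sided test would give 0.599. The figure is therefore the minimum detectable AUC against 0.5, two-sided, and it is correct.

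**3. Where significance starts.** 0.5 + 1.96 × √(0.0875/55) = 0.578. With the Mann-Whitney null variance, 583/(12 × 55 × 527), it is 0.580.

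**4. What a test at the sized AUC would do** (equal-variance binormal curve, illustrative). Specificity at 95% sensitivity = Φ(0.402 − 1.645) = 0.107. Share testing negative = (0.107 × 527 + 0.05 × 55)/582 = 0.102. About 10% of patients would be spared investigation.

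**5. The 3.5% comparison.**
- Sensitivity 80-95% means 5-20% missed; 70-87% means 13-30% missed. Neither range includes 3.5%.
- With 55 of 55 detected, the exact upper limit for missed cancers is 1 − 0.025^(1/55) = 6.5% two-sided, or 1 − 0.05^(1/55) = 5.3% one-sided.
- An upper limit of 3.5% with no misses needs ln(0.025)/ln(0.965) = 103.5, so 104 cases, or 104/0.095 = about 1,095 patients.
- The chance of no miss in 104 is 0.965^104 = 2.5% at a true sensitivity of 96.5%, and about 5 in 10 million at 87%.

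**6. What 582 patients deliver at the protocol's assumed accuracy** (Wilson 95% intervals, expected counts).

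| Measure | Expected | 95% interval |
|---|---|---|
| Sensitivity, upper assumption | 87% of 55 | 76-94% |
| Sensitivity, lower assumption | 70% of 55 | 57-80% |
| Specificity | 514/527 = 97.5% | 95.8-98.6% |
| NPV at 87% sensitivity | 514/(514 + 7.15) = 98.6% | 97.2-99.3% |
| NPV at 70% sensitivity | 514/(514 + 16.5) = 96.9% | 95.0-98.1% |

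**7. Would a success rule on sensitivity help?** The weak test of step 4, at 95% sensitivity, would detect about 52 of 55, with a Wilson lower limit of 85%. That exceeds the 76% lower limit that the hoped-for 87% sensitivity supports. A rule on sensitivity alone, without a fixed cutoff and a specificity floor, would pass the very test it was meant to stop.

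**The case for a change.** The strongest case for a change is that the protocol makes affirmative claims. It says the data will suffice and the power is adequate, while the objective is accuracy and the use is rule-out. An analysis plan does not undo such statements. The expected sensitivity and specificity stand in the same section as the power calculation and are not used in it. Section 5.1 calls two unlike figures comparable, on a matter that bears on the safety of a rule-out test. Correcting the wording would need no more patients, and a pilot label excuses a modest size but not an overstatement.

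Part of this stands. The 0.612 is not labelled as a minimum detectable AUC against 0.5, and the background comparison does not fit 5-20% missed, still less 13-30%.

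The rest does not carry. The sufficiency phrase sits in a generic list of conditions for ending the study and names no precision that 55 cases fail to reach. The sized test suits the hypothesis in section 10, that progastrin is a potential biomarker, and the ROC curve is part of the primary endpoint. Section 20 names an extended study as well as a pathway change, and nothing there equates a positive finding with rejecting 0.5. Because 10.2 reports sensitivity, specificity and predictive values beside the AUC, a marker with 11% specificity at 95% sensitivity would be plain to any reader. A success threshold is commonly left to the analysis plan, which is not at hand.

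**Conclusion.** No change to the plan follows. The stated power is delivered: 0.7999 against a target of 0.8, at a size the protocol openly derives from accrual. The 3.5% is a background comparator, not a criterion of this study, so failing to confirm it is not a failure against the study's own standard. Meeting it would need at least 104 cancers with none missed, about 513 more patients (1,095 − 582). At the 70-87% sensitivity the protocol assumes, 13-30% of cancers would be missed, and no sample size would bring that to 3.5%.

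For a pilot, 95% intervals of about 76-94% or 57-80% for sensitivity and roughly 95-99% for NPV are a fair return. Labelling the AUC or rewording the background would alter no estimate, test or decision. The loose comparison in 5.1 is a slip of wording.

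This rests on four assumptions: all 55 expected cancers are evaluable; the 3.5% is a share of cancers missed, as its place beside sensitivity suggests; the null is 0.5, inferred from the exact reproduction; and accuracy is as section 10.1 assumes. NPV also depends on the 9.5% prevalence and does not replace sensitivity.

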# 6.5. Secondary endpoint

Identification and proof of principle validation of novel TEs as potential biomarkers for colorectal cancer diagnosis.

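### The same 100 samples are assigned to both finding and validating the TE markers; only RNA-derived TEs have independent data named for validation

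*Protocol*

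**What the plan says.** The secondary endpoint (Protocol 6.5) is "Identification and proof of principle validation of novel TEs as potential biomarkers for colorectal cancer diagnosis". Validation is therefore half of what the endpoint promises.

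Section 10.1 fixes the material as "25 LGI cancer proven samples and 75 non-cancer (normal) samples", drawn from the 582 participants, and says that these "will be selected and tested for TEs in order to identify and validate novel biomarkers as potential tests for colorectal cancer diagnosis". The participant-number row of the synopsis (section 4) likewise gives both tasks to the one subset of 100. Neither place describes a division into a discovery part and a validation part.

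Section 8.2 adds a second source of data: "The TEs identified in this project to predict CRC will be also validated by testing it on publicly available additional cfRNA cohorts". It also plans a second platform: "Also Plasma DNA will be used for nanopore DNAseq (provides sequence variants and epigenetic modifications of DNA"). No external cohort is named for the DNA part.

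Section 10 says of the TE outcome that it "is exploratory and hence does not require formal power calculation". Section 20 nevertheless lists a paper on identifying and validating new TEs among the planned publications.

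**The concern.** When many candidate markers are ranked on a small sample, the best of them look good partly by chance. If their performance is then computed on the same patients, that chance is counted as signal. With only 25 cancers the effect is large. Selecting markers on all 100 samples and cross-validating afterwards hardly helps, because the held-out patients have already influenced the selection.

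At stake is what the secondary endpoint can conclude. A high AUC obtained within the 100 samples and reported as proof-of-principle validation would not separate a real TE signature from noise. DNA-derived markers are the most exposed, because the protocol names no other data in which they could be tested.

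**Working it through.** **The plan's own figures.** The protocol states no statistical figure for the TE subset, only the counts 25 + 75 = 100. The one power statement in 10.1 concerns progastrin: "Number of cases (GI cancer): 55 Number of controls (no cancer): 527 Area under the curve (AUC): 0.6118569", where "we aim to achieve a power of 0.8 and a significance level of 0.05". The one-curve ROC power formula with the binormal (Obuchowski) variance and two-sided alpha 0.05 gives AUC 0.61186 for 80% power, which agrees. The recruitment arithmetic agrees too: 18 × 2400/52 = 830.8; × 0.7 = 581.5; 9.5% of 582 = 55.3. So 25 cancers are a subset of about 55 expected. None of this covers the TE part.

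**Inputs for the TE check.**
- From the protocol: 25 cases and 75 controls.
- Assumed, because the protocol gives no number: K = 100, 1,000 or 10,000 candidate markers.
- Assumed: independent markers with no true signal, and a score that adds up the 10 best, each with its sign.

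**Step 1: one noise marker.** The standard error of its AUC is √[(n₁ + n₀ + 1)/(12 n₁ n₀)] = √[101/(12 × 25 × 75)] = √(101/22,500) = 0.067.

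**Step 2: many noise markers.** The expected number with unadjusted p < 0.05 is 0.05K, that is 5, 50 and 500. The chance of at least one is 1 − 0.95^K, which is 99.4% at K = 100 and practically 100% above that. Under a Bonferroni rule, a false hit occurred in only about 2% to 3% of simulated datasets.

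**Step 3: re-use against independent data.** Simulation with 300, 300 and 60 datasets for the three values of K gave these mean AUCs:

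| Candidates K | Best single marker, same 100 | 10-marker score, same 100 | 10-marker score, held-out half (12 vs 37) | 10-marker score, independent cohort (assumed 25 vs 75) |
|---|---|---|---|---|
| 100 | 0.68 | 0.85 | 0.50 | 0.50 |
| 1,000 | 0.73 | 0.93 | 0.51 | 0.50 |
| 10,000 | 0.76 | 0.97 | 0.49 | 0.52 |

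The last two columns have a true value of 0.50 by construction. The bottom row rests on only 60 datasets. In the independent cohort the noise score passed a one-sided 5% test in about 4% to 8% of runs.

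**Step 4: does cross-validation repair it?** A second simulation used a t-weighted 10-marker score and 150 null datasets for each K. A repeat run agreed within simulation error.

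| Candidates K | Same 100 | 5-fold, selection done beforehand on all 100 | 5-fold, selection repeated in each fold |
|---|---|---|---|
| 100 | 0.87 | 0.80 | about 0.50 |
| 1,000 | 0.94 | 0.91 | about 0.50 |
| 5,000 | 0.96 | 0.95 | about 0.50 |

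Only selection inside the folds gives the right answer.

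**Step 5: which markers have independent data?** RNA-derived TEs have the public cohorts of 8.2. For variants and epigenetic marks from nanopore sequencing the protocol names none, so for these the 100 samples are the only data in the document.

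**The case against.** The strongest reply is that external validation is already planned. The cohorts in 8.2 are separate from the 100 samples, and Step 3 shows that a noise score falls back to about 0.50 in such data. The phrase in 10.1 may simply compress the two stages of 8.2, identification here and validation there. The word *also* in 8.2 does not settle this, since that section uses it loosely. The protocol prescribes no analysis that scores the markers on the samples that selected them, and a split or nested cross-validation would be compatible with its wording. Resampling detail commonly belongs in a statistical analysis plan, which is not at hand. The candidate count and the scoring method are assumptions, and the aim is openly exploratory.

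Most of this stands, and it limits the point. A reader might infer that even pure noise would come out of this plan as validated, or that the TE endpoint will almost certainly show high discrimination. The documents do not support either statement: noise would be expected to fail in the public cohorts, and no same-sample analysis is laid down.

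The reply does not remove the text itself. The synopsis and 10.1 both give one set of samples both roles, and that is stated in the protocol rather than left open. Exploratory status excuses the missing power calculation; it does not turn same-sample performance into validation. It may be said that 8.2 promises no validation of DNA findings. If so, saying plainly that they are discovery only costs nothing.

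**Conclusion.** The point holds in limited form. Any validation claim made within the 100 samples would be unreliable. Under no signal, the apparent AUC of a 10-marker score is about 0.85 to 0.97, where independent data give about 0.50. The same limit applies to DNA-derived markers, which have no independent data named. It does not extend to RNA-derived TEs tested in the public cohorts, provided that the signature is fixed beforehand.

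The size rests on an assumed 100 to 10,000 independent candidates and on one type of score. Correlated markers would make the inflation smaller but would not abolish it. The figures show what re-use can do; they do not predict this trial's result. Whether the public cohorts resemble 2WW referrals cannot be judged from the protocol, and nothing here depends on it. The change is worth making because it alters what a named endpoint may claim and is cheap before analysis starts.

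**What to change.** In the synopsis, 8.2 and 10.1:

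1. Call the 100 samples a discovery set.
2. State that any performance figure from them comes from cross-validation in which TE selection and model fitting are repeated inside every fold.
3. Lock the RNA signature and its threshold before the public cfRNA cohorts are used, and reserve the word *validated* for that test.
4. Report findings from nanopore DNA sequencing as discovery only.

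The details of the cross-validation can sit in the statistical analysis plan, but the roles of the two data sources belong in the protocol. No new samples or assays are needed. The cost is a little more computing and a more modest TE claim, with internal performance figures likely to be lower.
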